3.2 Secondary Objectives

Aim 2. To identify clinically useful participant characteristics associated with outcome as a way of gaining an understanding of subgroups of participants for whom CBT is most beneficial.

Hypothesis 1: Variables such as treatment motivation at baseline and rapid treatment response will be positively associated with treatment outcome after the acute treatment phase of CBT and through follow-up periods.

Hypothesis 2: Interpersonal distress and extra-intestinal medical problems at baseline will be negatively associated with treatment outcome after the acute treatment phase of CBT and through follow up.

Aim 3. To identify theory-based change mechanisms (active ingredients) that explain how and why CBT achieves therapeutic objectives.

Hypothesis 1: Changes in the severity of IBS symptoms are partly mediated by changes in participants' beliefs regarding the causality (locus of control) and controllability (self efficacy) of IBS symptoms.

Hypothesis 2: Changes in the severity of IBS symptoms are partly mediated by nonspecific factors such as a strong therapeutic alliance and positive expectancy of improvement.

Aim 4. To describe the cost and cost effectiveness of MC-CBT, S-CBT and attention placebo for IBS.

Hypothesis 1: MC-CBT is associated with decreased direct and indirect cost compared to SCBT and associated with increased direct and indirect cost compared to attention control.

Hypothesis 2: MC-CBT will prove cost effective relative to either S-CBT or attention control.

Aim 5. To assess long-term durability of acute treatment effects of CBT at 3-, 6-, 9-, and 12 month follow-ups.

Hypothesis: Participants assigned to both CBT conditions will maintain treatment gains with respect to attention placebo through quarterly follow-up periods extending to 12 months after treatment completion.

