6.1 Standard CBT (S-CBT)

S-CBT is a skills-based training program ³ that involves 10 weekly, one-hour individual sessions. Treatment is structured around six overlapping phases:

- 1. Information and education regarding stress and its relationship to IBS
- 2. Self-monitoring of stressful situations associated with IBS episodes
- 3. Muscle relaxation exercises both to increase physiological self regulation and to cultivate a sense of mastery or self control over symptoms

- 4. Learning to identify, reevaluate, and change negatively skewed thoughts associated with IBS
- 5. Changing underlying schemas or "core" beliefs (e.g. perfectionism)
- 6. Formal training in problem solving to strengthen the ability to cope more effectively with realistic stressors associated with IBS weekly home exercises are assigned to facilitate skills acquisition.

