6.2 Minimal-Contact CBT (MC-CBT)

MC-CBT covers the same range of procedures featured in S-CBT but relies extensively on self-study materials to facilitate skills building. Additionally, whereas the S-CBT condition involves 10 one-hour clinic visits, MC-CBT meets for only four, one-hour clinic visits over a 10-week period.

- 1. At the first MC-CBT session, treatment is explained, self-study materials are provided and muscle relaxation and self-monitoring are introduced.
- 2. The second treatment session introduces cognitive coping techniques (e.g. decatastrophizing through prediction testing).
- 3. At the third session, participants learn problem-solving techniques and more advanced cognitive coping skills (e.g. modifying core beliefs such as perfectionism).
- 4. The fourth session introduces relapse prevention skills.

In the MC-CBT condition, two 10-minute phone contacts are scheduled at weeks 3 and 7 to troubleshoot around any problems encountered between clinic visits.

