The richness of the data can be illustrated by considering one example; namely, IBS self efficacy used to predict within-treatment variability in response to outcome at the immediate post-test (IM), pooling the MC-CBT and S-CBT groups to bolster the stability of parameter estimates. IBS self efficacy is measured at baseline (BA) and during weeks 1, 3, 5, 7, 8 and 12 of the acute treatment phase (i.e. W1, W3, W5, W7, W8, W12). There are several plausible mediation models that may bear on results. An *early* response mediation model states that IBS self efficacy gains experienced early in treatment (e.g. from B to W1 and W3) are the primary determinants of the ultimate response to treatment at IM. A recency mediation model states that the level of IBS self efficacy at the last treatment session (W12) is the primary mediator of IM response to treatment. A growth curve mediation model states that it is the general acceleration/deceleration of IBS self efficacy across the acute treatment phase (as well as the shape of the curve) that best predicts response to treatment at IM (with IBS self efficacy being as parameterized as a growth curve per Figure 1). A fourth model is one that incorporates all three types of mediational influence into a single estimating equation, with linear coefficients attached to each to reflect their relative influence in impacting treatment response. The baseline outcome variable is used as a covariate and the IM outcome is used as the criterion. It is possible to use the M Plus software to parameterize all three sources of influences and then test their relative contributions. Note that this can be done to predict response to treatment as measured at IM or it can be used to predict decay functions characterizing change from IM to FU12. Models also can be pursued that include multiple mediators in the same model, thereby permitting complex multivariate explorations of the data.

Aim 4

The following section outlines the steps for the economic analysis of the costs and costeffectiveness of S-CBT and MC-CBT relative to the attention control group.

Aim 4A (Cost Hypothesis): The MC-CBT intervention will have lower costs per person than the S-CBT.

Aim 4B (Cost Hypothesis): Both S-CBT and MC-CBT will be cost-effective relative to the less costly but also less effective attention control. MC-CBT will be at least as effective as S-CBT, and given its lower costs, MC-CBT will be cost-effective relative to S-CBT.

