Hypotheses 4A and 4B require us to estimate the costs of each intervention and then to combine the cost and effectiveness data to estimate the cost-effectiveness of each intervention relative to the studied alternatives. Cost-effectiveness analysis compares the differences in cost with effectiveness across alternative policy options. The results are expressed as the incremental cost per unit of incremental outcome change, yielding ratios such as the incremental cost per reduction in health care utilization (e.g. days of inpatient hospital stay).

Cost Collection

To perform a cost-effectiveness analysis, we need estimates of both the effectiveness of the interventions and the costs of each intervention. Because most of the data required for the cost-effectiveness analyses will already be collected for the effectiveness analysis, we will estimate the costs of the interventions, regardless of whether the interventions are found to be effective. Our cost study methodology will follow the micro-costing approach recommended by [23] and [24] and which was implemented in [25] and [26] for costing of methadone treatment services and in [26] in the context of the Combining Medications and Behavioral Interventions for Alcoholism (COMBINE) randomized control study of alternative alcohol treatments. This approach identifies, measures, and values the resources associated with each activity of the intervention. Our primary perspective for the cost analysis is the provider and includes only the provider costs and excludes costs incurred by private consumers or households. We recognize that the societal perspective is often cited as the appropriate perspective to use [23-24]; however, as there is no social decision maker, most costeffectiveness analyses adopt the provider perspective to make the analysis more relevant to real-world situations. However, another primary decision-maker is the participant. Few studies consider the participant's perspective in estimating costs and cost-effectiveness even though these costs may have a substantial impact on a participant's treatment choice, his or her ability to access treatment, or his or her treatment adherence. As part of our sensitivity analysis, we will expand our analysis to estimate participants' costs such as time, travel expenses, and out-of-pocket health care expenses and to analyze the impact these costs have on the interventions' costeffectiveness.

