Estimating the costs directly attributable to the intervention conditions requires collecting both variable and fixed costs incurred in providing the interventions. Variable costs vary directly with the services provided and include time spent providing participants with M-CBT or S-CBT sessions and the cost of session materials. Fixed costs do not vary with the provision of services; they include expenditures on building space, utilities, and general office supplies.

The first step in conducting this type of cost analysis is to define fully the interventions being delivered and to identify all the associated activities. Once intervention activities are identified, the next step is to identify the resources that may be used to deliver the intervention (e.g. type of labor, space). The final step is to identify the costs of the resources used in the intervention. The analysis will make a distinction between one-time startup costs and ongoing implementation costs.

Cost Analysis

Once data on resources used and the unit costs of those resources are gathered, we will derive cost estimates for various intervention activities, including both startup and ongoing implementation activities, following the methodology in ²⁷. The labor costs of each activity are equal to the product of the amount of time spent by each person on the activity and his/her hourly wage. For salaried staff, salary will include the actual hourly wage plus a fringe rate that covers all benefits. To estimate space costs, the size of the room used for each activity will be multiplied by the annual market rental price per square foot prorated by the time for which the room is used for that activity. Finally, we will multiply the unit cost of materials used during the delivery of the intervention with the quantity used per intervention session. For each participant in a given intervention, the total cost of the intervention is simply the cost per activity multiplied by the number of activities or services received by the participant during the intervention, and taking the mean across participants in a given intervention yields the mean per-participant cost of that intervention.

Cost-Effectiveness

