The **Client Satisfaction Questionnaire-8** (CSQ-8) ⁸³ is an eight-item instrument of general satisfaction with treatment. It will only be administered at week 12. In addition, respondents will complete a single-item treatment satisfaction scale ("During the past week, how satisfied are you with the level of IBS relief your current treatment provides?"), with treatment responses ranging from 0 = very dissatisfied to 4 = very satisfied, that will be embedded in the end-of-week section of the daily diary.

Health Care Utilization/Cost

A critical component of the study is an economic evaluation (e.g. cost, costeffectiveness, and benefit-cost analyses) of the CBT treatment options. Some of the data needed for the economic evaluation will be collected in the **Economic Form-IBS**⁸⁴. This form includes a series of questions on health status and activity limitations, labor market activity, and health care insurance coverage. In addition, the form collects detailed information on health care utilization including the type and amount of new, or previously administered, treatments (including prophylactic), their focus, and associated costs (e.g. direct costs for diagnosing, treating, prescriptions, OTC agents, physician visits, alternative and complementary therapies) and patient costs of accessing these services (e.g. transportation, child care). Information from this form will be used to estimate the economic benefits and costs associated with the CBT treatment options. We will administer the Economic Form-IBS at major assessment periods (baseline, post-acute treatment phase, and quarterly follow-up visits).

Treatment Mediator Assessment

This set of measures is designed to help clarify the psychological processes that explain why CBT works or how it produces change (i.e. active ingredients) in IBS symptoms. These measures are completed at regularly scheduled times during the active treatment phase and at follow-up periods.

Control Beliefs

The 25-item **IBS Management Self Efficacy Scale** (IBS-SE) measures participants' confidence in their ability to control and manage IBS episodes using a seven-point Likert scale (1 = strongly disagree, 7 = strongly agree) ⁴¹. The **IBS-Specific Locus of**

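### Aim 4 Hypothesis 1 is about direct and indirect cost, but the primary cost analysis in 7.4 measures only the provider's cost of delivering treatment and so cannot test it

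*Protocol*

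**What the plan says.** Section 3.2, Aim 4 Hypothesis 1, states that "MC-CBT is associated with decreased direct and indirect cost compared to SCBT", and that MC-CBT has higher direct and indirect cost than attention control.

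Section 7.4 restates the first part as Aim 4A: "The MC-CBT intervention will have lower costs per person than the S-CBT". The words direct and indirect are gone. Under Cost Collection the provider perspective is primary, and the analysis "includes only the provider costs and excludes costs incurred by private consumers or households". Variable costs "include time spent providing participants with M-CBT or S-CBT sessions and the cost of session materials"; fixed costs cover space, utilities and office supplies. Under Cost Analysis, "the total cost of the intervention is simply the cost per activity multiplied by the number of activities or services received by the participant". Under Cost-Effectiveness, these same costs are combined with effect measures to form the ICERs and CEACs.

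Participant costs such as time, travel and out-of-pocket care are assigned to a sensitivity analysis.

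Appendix 8 (Health Care Utilization/Cost) describes an Economic Form that records health care use, its costs and labour market activity. Of this form it says: "Information from this form will be used to estimate the economic benefits and costs associated with the CBT treatment options". Appendix 7 schedules the form at baseline and at all five follow-ups.

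**The concern.** The hypothesis and the variable meant to test it do not match. Under the costing formula, the main thing that varies between participants within an arm is how many activities they received. Nothing that happens to a participant's health care use or work afterwards changes that participant's cost. The indirect part of the hypothesis has no place in the primary analysis, and the direct part is reduced to delivery.

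What is at stake is the reading of a secondary aim. A report could state that Hypothesis 1 is supported when all that has been shown is that four sessions and two short calls cost less to deliver than ten sessions. The same delivery saving then becomes the numerator of every cost-effectiveness ratio, with no offset for care or work loss in either direction.

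**Working it through.** The protocol gives no expected difference, power or precision for Aim 4, so there is no figure to reproduce. The check applies the 7.4 formula to the schedules.

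**Inputs**
- S-CBT (6.1): "involves 10 weekly, one-hour individual sessions", so 10 × 60 = 600 minutes.
- MC-CBT (6.2): "MC-CBT meets for only four, one-hour clinic visits over a 10-week period", plus two 10-minute calls, so 4 × 60 + 2 × 10 = 260 minutes.
- Attention control (6.3): the same format as MC-CBT, so 260 minutes.
- 160 participants per group (7.4, Equivalence Testing).
- Price: 8.1 mentions $90 for a 50-minute session. This is a background charge, not the wage-plus-fringe costing of 7.4, and serves here only as an illustration.

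**Scheduled gap.** 600 − 260 = 340 minutes; 260/600 = 0.433, a 57% saving before any data are collected.

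**Break-even attendance.** With MC-CBT fully attended, therapist time is equal when S-CBT participants average 260/60 = 4.3 of 10 sessions. At 80% MC-CBT attendance the break-even falls to 0.8 × 0.433 = 35% of S-CBT sessions.

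**Equal per-session attendance in both arms.** Assume treatment ends after two consecutive missed sessions (Appendix 6 gives this as an example of noncompliance that may lead to withdrawal) and that both MC-CBT calls always take place. Expected therapist minutes are:

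| Attendance per session | S-CBT | MC-CBT |
|---|---|---|
| 95% | 565 | 248 |
| 80% | 424 | 207 |
| 60% | 232 | 149 |
| 40% | 102 | 95 |
| 30% | 62 | 72 |

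The order reverses only near 30%.

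**Chance of a significant result.** Take S-CBT attendance at 50%, independent across sessions, and MC-CBT at 100%. The means are 300 and 260 minutes. The S-CBT SD is 60 × √(10 × 0.5 × 0.5) = 94.9, the SE is 94.9/√160 = 7.5, and z = 40/7.5 = 5.3. In simulation, MC-CBT was significantly lower in 99.9% of trials in this case and in about 100% at S-CBT attendance of 60% to 90%. If S-CBT attendance were instead all-or-nothing at 50%, the SD would be 300, the SE 300/√160 = 23.7, z = 1.69, and the chance about 39%.

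**In money.** 340/60 × $90 = $510 per participant if $90 buys an hour, or 340/50 × $90 = $612 if it buys 50 minutes. At an assumed $50 to $150 per hour the range is $283 to $850. A difference of more than this in health care and work-loss cost, favouring S-CBT, would reverse the sign of total cost.

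**Attention control.** 260 − 260 = 0 scheduled minutes. The second half of Hypothesis 1 therefore turns on attendance, materials, staff wages and start-up cost.

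**Precision of a total-cost comparison.** The protocol gives no SD for total cost. The 95% half-width is 1.96 × SD × √(2/160):

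| Assumed SD | Half-width | Power for $510 |
|---|---|---|
| $1,000 | $219 | 99.5% |
| $2,000 | $438 | 63% |
| $3,000 | $657 | 33% |
| $5,000 | $1,096 | 15% |

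**The case against.** The provider perspective is declared and argued for in 7.4, with the societal alternative openly considered. Micro-costing of delivery answers Aim 4A exactly as 7.4 words it. That stands: the perspective is not an error, and narrowing section 3.2 would remove the conflict.

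A reader might infer that worse health care use under MC-CBT would go unseen. The documents do not support that. Change in health care use is a secondary endpoint (3.4) and is covered by the Aim 1 hypotheses (3.1). Section 7.4 also gives reduced utilization as an example of an ICER outcome unit. Appendices 3 and 8 mention a benefit-cost analysis in which offsets might be valued, though without a method. What remains is narrower: such a difference does not enter the primary cost comparison or the ICER numerator.

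A reader might also infer that the cost conclusion is wholly predetermined. It is not. Cost counts activities received, and materials and start-up are included. Clustered dropout could weaken the contrast, as the 39% case shows. The attention-control comparison is not decided by the schedule, and Aim 4B also depends on the difference in effect.

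The participant-cost list in the sensitivity analysis is illustrative, so some indirect cost may be covered there. Insurer-paid care is not a participant cost, however, and a sensitivity analysis is not the test of the hypothesis. A separate analysis plan may give valuation detail, but the protocol itself fixes the primary cost variable, and that variable conflicts with section 3.2.

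**Conclusion.** The mismatch is real and confined to a secondary aim; the primary endpoint is not affected. Followed as written, 7.4 estimates delivery cost and leaves the direct-and-indirect-cost hypothesis untested. For MC-CBT against S-CBT the delivery result is all but set by the 340-minute scheduled gap over any plausible range of attendance. For MC-CBT against attention control it is near a tie on contact time. The minutes come straight from the protocol's schedules. The dollar figures rest on an illustrative price, the attendance results on the stated attendance models, and the precision figures on assumed SDs and complete data.

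**What to change.** Keep the provider analysis and label it as delivery cost. Add, as the test of Hypothesis 1, a prespecified total-cost comparison to 12 months: delivery cost, health care use from the Economic Form valued at unit costs whoever pays, and productivity loss from the labour market items. Report each component and the total by arm, with bootstrap intervals. Give matching ICERs and CEACs for effect measures other than health care utilization, because valuing utilization in the numerator while using it as the outcome unit would count it twice.

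At minimum, narrow Hypothesis 1 in section 3.2 to intervention delivery cost, and state in 7.4 where the Economic Form data are used.

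No new data collection is needed. The cost is unit-cost valuation and extra analysis. The downside is precision: total cost varies more than delivery cost, so the interval will be wider and the comparison may be inconclusive.

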7.4. Formal Data Analysis

Aim 1

The primary focus of Aim 1 is to establish whether the effects of MC-CBT and S-CBT are comparable. We will pursue this from two perspectives: a traditional hypothesis testing framework and an equivalence testing framework. For the core outcome variables, we have assessments at baseline (BL), immediate post-test (FU W12) and at three-, six-, nine-, and 12-month follow-ups (FU3, FU6, FU9 and FU12) for each of three groups (MC-CBT, S-CBT and the active comparison control (attention control)). The traditional analysis for a given outcome variable is a two-way analysis of covariance

using the three groups as a between-participants factor, time as a within-participants factor (IM, FU3, FU6, FU9 and FU12) and the baseline score as a covariate. Single degree of freedom contrasts focus on the pair-wise comparisons of adjusted means within a given time period (e.g. comparing MC-CBT, S-CBT, and the attention control condition). Of interest is whether there are statistically significant pair-wise contrasts between the groups. We will pursue such contrasts using non-pooled error terms across time (because of the likely violation of sphericity), but with pooled error terms across groups within time (unless diagnostics suggest otherwise). We will use the program M Plus to estimate the single degree of freedom contrasts (by translating the analysis of covariance model into an SEM framework). M Plus has the capability to take into account cluster effects, should that be necessary, and it also offers robust algorithms.

In terms of statistical power, for a single degree of freedom contrast between two independent groups with a single covariate, the approximate sample size needed to achieve power of 0.80 for an adjusted mean difference of d = 0.50 (using Cohen's d) is approximately 65 per group. To achieve power of 0.90 requires a sample size of 85 per group. Our sample sizes easily meet these standards.

Aim 5

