In the event that the two studied interventions are effective relative to the attention control group, we will implement a cost-effectiveness analysis. Our cost-effectiveness methodology will follow the approach described in the literature ^{23, 28-29} and that has been implemented in ^{26, 30-31} in the context of randomized control trials (RCTs). We will combine the cost estimates described above with intervention effectiveness measures of changes in outcomes related to IBS. To perform the cost-effectiveness analysis, the costs and outcome measure for each intervention under study will be tabulated in increasing order of effectiveness (or cost). Starting with the intervention with the smallest effectiveness (or cost), cost-effectiveness ratios will then be computed for each intervention relative to the next most effective option after eliminating intervention options that are dominated by other interventions ^{23, 32}. To derive the cost-effectiveness ratios, we will calculate the difference in costs and outcomes between each intervention. The incremental cost-effectiveness ratio will then be calculated as the ratio of the difference in costs to the difference in outcomes. An intervention may be dominated in either a simple sense (higher cost and lower effectiveness than another option) or in an extended sense (higher cost-effectiveness ratio than a more effective option). In either case, the cost of achieving a given level of the outcome is lower if the dominated intervention is eliminated.

We will calculate cost-effectiveness acceptability curves (CEACs) as an alternative to confidence intervals for ICERs ³³⁻³⁴. The CEACs incorporate the inherent variability of the cost and effectiveness estimates and they show the probability that an intervention is the most cost-effective as a function of the policymaker's intrinsic valuation or willingness to pay for the outcome. We will use nonparametric bootstrap methods to calculate CEACs. (See also ^{26, 35-36}.)

Sensitivity Analysis

After we have conducted the CEA, we will conduct a sensitivity analysis. The objective of a sensitivity analysis is to assess whether the cost-effectiveness results are affected

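### The cost-effectiveness analysis hangs on an undefined efficacy condition that Aim 4 does not contain, so Hypothesis 2/4B may go unanswered

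*Protocol*

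**What the plan says.** Section 3.2 of the protocol sets Aim 4 as "To describe the cost and cost effectiveness of MC-CBT, S-CBT and attention placebo for IBS". Its Hypothesis 2 is that "MC-CBT will prove cost effective relative to either S-CBT or attention control". Neither statement depends on an efficacy result.

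Section 7.4 restates the economic hypotheses as 4A (costs) and 4B (cost-effectiveness of each CBT arm against control, and of MC-CBT against S-CBT). It then says: "Hypotheses 4A and 4B require us to estimate the costs of each intervention and then to combine the cost and effectiveness data". Again no condition is attached. Under Cost Collection it adds: "we will estimate the costs of the interventions, regardless of whether the interventions are found to be effective".

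The condition appears only under Cost-Effectiveness in section 7.4: "In the event that the two studied interventions are effective relative to the attention control group, we will implement a cost-effectiveness analysis". No endpoint, time point, test or threshold is given. Nothing is said about the case where one arm, or neither, is effective. The same subsection then plans dominance rules, incremental ratios and bootstrap uncertainty: "We will calculate cost-effectiveness acceptability curves (CEACs) as an alternative to confidence intervals for ICERs".

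**The concern.** An unconditional aim has been tied to a conditional analysis. On a plain reading, the two studied interventions are MC-CBT and S-CBT, so both must be effective before costs and effects are combined. That combining step is what Hypothesis 2/4B needs. One of its comparisons, MC-CBT versus S-CBT, does not depend on either arm beating control.

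Two things are at stake. First, the cost-effectiveness hypothesis may not be addressed, and if exactly one arm is effective the protocol gives no rule at all. Second, any condition judged on the trial's own data selects on the observed effect. The analyses that go ahead would tend to start from favourable CBT-versus-control estimates. Because effectiveness is undefined, the decision to proceed could also be made after the results are seen.

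**Working it through.** **Inputs from the protocol.** Planning effect d = 0.50, with about 65 per group for 80% power and 85 for 90% (section 7.4, Aim 1). Planned size 160 per group (section 7.4, Equivalence Testing). Allocation 1:1:1 (section 2).

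**Assumptions.** Two-sided alpha of 0.05, as the sample size passage states none. A continuous outcome with SD 1. Effectiveness read as both CBT-minus-control contrasts significant in favour of CBT. Effects other than 0.50 are shown as a range.

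**Reproducing the protocol's figures.** n per group = 2(z₀.₉₇₅ + z_power)²/d².
- 80% power: 2(1.960 + 0.842)²/0.25 = 62.8, so 63 (stated: about 65).
- 90% power: 2(1.960 + 1.282)²/0.25 = 84.1, so 85 (stated: 85).

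The stated sizes are consistent with the assumed alpha.

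**Chance of meeting the condition.** With 160 per arm, the standard error of each contrast is √(2/160) = 0.1118, so significance needs an observed difference above 1.96 × 0.1118 = 0.219. The contrasts share the control arm, so their correlation is (1/160)/(2/160) = 0.5. The expected z is d/0.1118: 4.47 at d = 0.50, 3.58 at 0.40, 2.68 at 0.30 and 1.79 at 0.20. Simulating the three arm means (2,000,000 draws) gives:

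| True d (two CBT arms) | Analysis run | Analysis skipped | Exactly one arm significant | Mean estimated d when run |
|---|---|---|---|---|
| 0.50, 0.50 | 0.989 | 1% | 1% | 0.503, 0.503 |
| 0.40, 0.40 | 0.908 | 9% | 8% | 0.416, 0.416 |
| 0.30, 0.30 | 0.641 | 36% | 25% | 0.353, 0.353 |
| 0.20, 0.20 | 0.268 | 73% | 33% | 0.313, 0.313 |
| 0.20, 0.40 | 0.428 | 57% | 52% | 0.302, 0.454 |

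**Effect of selection on CBT versus control.** The inflation is 0.503/0.50, under 1%, at the planning effect; 0.353/0.30 = 1.18 at d = 0.30; and 0.313/0.20 = 1.57 at d = 0.20.

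**Effect of selection on MC-CBT versus S-CBT.** With equal true effects, the conditional means are equal, so the difference is unbiased. With true effects of 0.40 and 0.20, the mean difference when the analysis is run is 0.454 − 0.302 = 0.152, against a true 0.20. It is pulled towards zero.

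**Fewer evaluable participants.** With 120 per arm (an assumption; the sample size passage gives no post-randomization loss), the analysis is run in 95% of trials at d = 0.50, 49% at 0.30 and 19% at 0.20.

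**The case against.** The strongest reply is that the sentence in section 7.4 does not say *only if*, names no p-value, and does not cancel the analysis otherwise. Elsewhere the protocol treats the economic evaluation as a critical component (Appendix 8, Health Care Utilization/Cost), and Appendix 3 provides for cost-effectiveness analyses as appropriate. That the condition is a significance test is therefore an inference. Section 7.4 makes it a natural one, since for Aim 1 it says: "Of interest is whether there are statistically significant pair-wise contrasts between the groups". But the percentages above illustrate one reading and are not fixed properties of the plan. The primary endpoint is also a binary responder measure (section 3.3), whereas the calculation uses a continuous outcome, as the protocol's own power statement does. What remains is a stated condition, undefined and at odds with the aim, with no other route to the analysis.

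A reader might also infer more than the protocol supports:
- *That all of Aim 4 may go unanswered.* It may not. Costs are estimated "regardless of whether the interventions are found to be effective", so Hypothesis 1/4A is covered, and effects are still estimated under Aim 1. What can be lost is the formal combination of the two.
- *That selection makes every incremental effect too favourable.* It does so only for CBT versus control. Even there, the inflation is on the gating outcome. If the cost-effectiveness outcome differs (section 7.4 mentions inpatient days; section 3.4 lists QALYs), it carries over only as far as the two are correlated.
- *That skipping is the typical result.* At the protocol's own planning effect it almost never happens. Smaller effects remain plausible, because section 8.1 describes results against attention controls as weaker than those against passive controls.
- *That the analysis is lost exactly when it matters most.* This is not shown. If the estimates make MC-CBT both cheaper and more effective than S-CBT, the planned dominance logic settles that comparison without a ratio.

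**Conclusion.** The inconsistency is real and lies in the text: section 7.4 attaches an undefined efficacy condition to an analysis that section 3.2 and Hypotheses 4A/4B promise without one. The exposure is confined to Hypothesis 2/4B. It does not touch the primary efficacy conclusion, the cost comparison or data collection.

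Its size depends on the true effects: negligible at d = 0.50, and substantial at 0.20 to 0.30 or when the two CBT arms differ. These figures rest on the significance reading, two-sided 5%, a continuous outcome and 160 evaluable per arm. The textual conflict needs none of those assumptions. The condition is also unnecessary, because dominance rules, incremental ratios and bootstrap acceptability curves already accommodate small, uncertain or negative effects. The passages should be reconciled.

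**What to change.** In section 7.4, Cost-Effectiveness, delete the opening condition. State instead that incremental costs, incremental effects and bootstrap acceptability curves will be estimated for all three randomized arms, including MC-CBT versus S-CBT, whatever the efficacy results. This brings the subsection into line with Aim 4 in section 3.2 and with Hypotheses 4A/4B.

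The cost is one sentence and slightly more analysis. No new visits or forms are needed: section 7.4 says most of the data will be collected for the effectiveness analysis anyway, and Appendix 7 schedules the economic form and EQ-5D at baseline and at every follow-up.
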